8.6. Long Term Clinical Follow-Up Chart Review

After completion of the 30-day Follow-up Visit, a retrospective Long Term Clinical Follow-Up Chart Review will be performed to collect up to 24 months of standard of care clinical information (if applicable). There are no office or telephone visits required. The Investigator or study coordinator will review the hospital charts to assess patient status and extract PCL characteristic pertaining to Morphological Status, Cytopathological Status, Biochemical Status, and Surgical Pathology. No new Adverse Event information will be captured after the 30 Day Post Procedure.

9. Statistical Considerations

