7.5. Adverse Event Assessment

- Immediate Adverse Event assessment: Assessment for immediate complications during the procedure and prior to discharge (approximately 2hrs post-procedure) or planned hospital observation transfer will be done and will be recorded on the *Adverse Event (AE) CRF*.
- Delayed Adverse Event assessment: Assessment for delayed complications will be done by telephone at 30 days (\pm 5 days) and will be recorded on the *AE CRF*. If a scheduled office visit is made during the same time window, it may substitute for the telephone call. If surgery or other major intervention (e.g., ERCP, other invasive biopsy) is performed prior to 30 days, events will be censored at the date of the procedure.

Adverse event details including definitions, types, and reporting requirements are provided in **Section 10**.

8. Study Visits

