8.3. Procedure

8.3.1. Lesion Characteristics

The following lesion characteristics will be assessed by EUS prior to the start of the FNA procedure and will be recorded on the *Procedure CRF*:

- a. Cyst size (maximal diameter, and cross-sectional diameter)

NOTE: In the case of a multilocular cyst, size will be measured both as the aggregate size of all cyst locules and the long and short perpendicular axis of the largest locule.

- b. Number of locules (1, 2, 3, 4, 5, 6-10, > 10)
- c. Presence of visible mucin (floating, or mobile filling defects)
- d. Presence of mural nodule (non-mobile filling defect) and size
- e. Presence of solid components
- f. Presence of distinct PCL wall
- g. Connectivity to pancreatic duct
- h. Maximal pancreatic duct diameter

An EUS image of the patient's PCL will be saved during the procedure.

8.3.2. *EUS-FNA Procedure*

The EUS-FNA procedure will be carried out in line with the guidelines provided in **Section 7** above, and the following data will be collected and recorded on the *Procedure CRF*:

- a. Route of access (gastric, duodenal, esophageal)
- b. Ease of insertion of EUS-FNA needle through echoendoscope
- c. Ability to reach target lesion
- d. Ability to penetrate into target lesion
- e. Quality of needle visualization
- f. Number of needle passes
- g. Ease of removal of EUS-FNA needle from echoendoscope
- h. Aspirate characteristics and adequacy of aspirate volume to perform two assays (cytology and CEA)
- i. Adverse Event assessment during procedure and through 2 Hours Post-Procedure or discharge from endoscopy unit

8.4. **Cytology and Chemistry Results**

The results of cyst aspirate cytology and CEA assessments will be provided by the cytology and chemistry labs and will be recorded on the *Cytology and Chemistry Results CRF*. Results will be categorized as follows⁴ and will be used for determination of Disease State per EUS-FNA:

- Cytology
 - Bland PAS +
 - Mucinous
 - Pigmented histiocytes
- CEA (ng/mL)
 - < 0.5
 - > 0.5 and < 200
 - > 200

8.5. **30-Day Follow-up**

The post-procedure 30-day Follow-up Visit will be conducted over the telephone. The visit window allows for this visit to occur anytime from 25 days to 35 days post procedure. Patients will be assessed for potential adverse events that might have occurred from discharge until 30 days post-procedure. AE information will be recorded on the *Adverse Event CRF*.

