10.1. Anticipated Adverse Effects

As per the commercial DFU included with the study devices, the potential complications associated with the use of the Expect Needle may include, but are not limited to:

- Bleeding
- Perforation
- Pancreatitis
- Infection
- Peritonitis
- Inflammation
- Aspiration
- Fever
- Allergic Reaction to Medication
- Hypotension
- Respiratory Depression or Arrest
- Cardiac Arrhythmia or Arrest
- Tumor Seeding

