10.4. Reporting Requirements to Sponsor

10.4.1. *Communication Method*

Reporting of adverse events and device deficiencies or malfunctions as outlined by category and as applicable during the entire duration of the study, from signing of the ICF through completion of an end-of-study report, should be made by entering pertinent information into the associated study data base fields. In case access to the electronic case report forms is not possible, the Investigator or site study staff members should contact the Sponsor Global Safety Office and Sponsor Project Manager by e-mail. If e-mail communications are also impossible, then one of these Boston representatives should be contacted by telephone. Contact information for the Sponsor Global Safety Office and Sponsor Project Manager will be provided and kept up to date by Sponsor at all times.

Upon receipt of these communications, associated source documentation may be requested by the Sponsor Global Safety Office and Sponsor Project Manager.

10.4.2. *Communication Timelines*

The following should be reported to Sponsor within 2 business days:

- All Serious Adverse Events (SAEs), whether related to the EUS-FNA devices and/or procedure or not
- Device Deficiencies, Failures, Malfunctions, and Product Nonconformities that led to any Adverse Event (AE) or Serious Adverse Event (SAE).

The following should be reported to Sponsor **within 10 business days**:

- All non-serious Adverse Events (AEs) related to the EUS-FNA devices and/or procedure
- Device Deficiencies, Failures, Malfunctions, and Product Nonconformities that did not lead to an Adverse Event (AE) or Serious Adverse Event (SAE).

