Pseudocyst	Pigmented histiocytes	< 200

* This cytological assay might be replaced by another cytological assay as needed

In order to assess the accuracy of EUS-FNA-based standard assays (cytology and CEA) as a diagnostic measure of disease state, the *Disease State per EUS-FNA* measure will be compared to a reference diagnosis. The reference diagnostic standard will be diagnosis from a surgical specimen histology, the true gold standard for cases that evolve to surgical resection within the 30 day follow-up time of the protocol. For cases that do not progress to surgery within 30 days of the EUS-FNA procedure, the reference diagnostic standard will be a composite diagnosis by a consensus board. The consensus board will consist of 3 to 5 Investigators who will be blinded to the type of needle used. The diagnosis of disease state

will be based solely on baseline medical history and EUS and cross sectional imaging of the cyst. Information regarding aspirate characteristics and results from aspirate tests will not be provided to the consensus board. Diagnoses will be rendered at a separate Investigators Meeting or virtual meeting.

- “*Disease State per Histology*”: This is the reference diagnostic standard. This measure is derived from the histology results of the surgical specimen in cases that progress to surgery within 30 days. Cysts will be classified as follows: *serous cyst*, *mucinous cyst*, *IPMN*, *pseudocyst*, or *Indeterminate*. As described above, this measure will serve as the gold standard for assessing diagnostic accuracy.
- “*Disease State per Consensus Board*”: This is the surrogate for the reference diagnostic standard. This measure is derived by the consensus board as described above. Cysts will be classified as follows: *serous cyst*, *mucinous cyst*, *IPMN*, *pseudocyst*, or *Indeterminate*. The classification will be based on baseline medical history and EUS and cross sectional imaging. Medical history will include, but not be limited to presence or absence of prior necrotizing pancreatitis, trauma or other potential cause of pseudocyst. Imaging will pertain to cyst location and cyst appearance.

Degree of correlation between *Disease State per EUS-FNA* and *Disease State per Consensus Board or per Histology* is illustrated below.

Total number of patients enrolled is sum of all entries, namely

$$\text{TOTAL} = A + B + C + \dots + S + T + U + V + W + X + Y.$$

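### Three separate day-30 rules keep data the trial already collects out of its accuracy and safety conclusions

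*Protocol*

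**What the plan says.** **Reference standard for endpoint h.** Protocol Appendix C.3 calls surgical histology "the true gold standard for cases that evolve to surgical resection within the 30 day follow-up time of the protocol". SAP 5.1.2 carries the same limit. All other patients are scored against a consensus board that sees baseline history, EUS and cross-sectional imaging, and no aspirate results.

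**Chart review.** Under Protocol 8.6 a "Chart Review will be performed to collect up to 24 months of standard of care clinical information", and surgical pathology is among the items extracted. In Figure 3 surgical pathology is marked only in the chart-review column. The follow-up schedule in SAP Section 1 stops at the 30-day contact and does not list the chart review.

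**Adverse events.** Protocol 8.6 adds: "No new Adverse Event information will be captured after the 30 Day Post Procedure". Section 10.4.1 has events reported "from signing of the ICF through completion of an end-of-study report". Section 10.1 includes "Tumor Seeding" among the potential complications of the needle.

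**The follow-up call.** Protocol 8.5 says: "The visit window allows for this visit to occur anytime from 25 days to 35 days post procedure". The same section asks about "adverse events that might have occurred from discharge until 30 days post-procedure". Under 7.5, if surgery or another major intervention comes before day 30, "events will be censored at the date of the procedure".

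**The concern.** Diagnostic accuracy for mucinous versus non-mucinous cysts is part of the stated primary objective. A patient resected in month 4 has definitive tissue in the study database, yet is scored against an imaging-based opinion. Accuracy is then measured against the weaker of two references in hand, and the plan offers no comparison to show whether that matters.

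On safety, staff will read charts that contain morphology, cytopathology and surgical pathology, which is where a late needle-related event such as seeding would appear. Section 8.6 tells them not to record it and 10.4.1 can be read as telling them to. Sites may resolve this differently. Under the 8.6 reading, an absence of seeding in endpoint a would say little about seeding.

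The early edge of the call window matters less. It bears on the 30-day rates of pancreatitis, infection and hemorrhage, which Section 10.8 compares with preset thresholds.

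**Working it through.** The plan gives no figure to reproduce here. The check sets the passages side by side and adds arithmetic for scale.

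**1. Histology**

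- Collected: surgical pathology, up to 24 months (8.6 and Figure 3).
- Used as reference: resections within 30 days only (C.3, SAP 5.1.2).
- Analysis of the remainder: none is named. SAP 5.6.2 promises descriptive summaries of post-procedure data collected under the protocol schedule. At most that yields a table of late pathology, and it does not link late pathology to endpoint h.

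The board may return Indeterminate, and the overall agreement formula [A+B+C+D+Y]/TOTAL counts cell Y, where both sources are Indeterminate, as agreement. A patient with a definitive late histology can therefore score as agreement because both the aspirate and the board were uninformative.

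For scale, let r be the share of the 250 patients resected by 24 months and f the share of those resected within 30 days. The documents give neither. Histologies used = 250 × r × f, and histologies collected but not used = 250 × r × (1 − f).

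| r (assumed) | f (assumed) | Used | Not used |
|---|---|---|---|
| 5% | 50% | 6.25 | 6.25 |
| 5% | 10% | 1.25 | 11.25 |
| 10% | 30% | 7.5 | 17.5 |
| 20% | 50% | 25 | 25 |
| 20% | 10% | 5 | 45 |

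Over these assumptions the unused number runs from about 6 to 45. It is never smaller than the number used, but that follows from taking f at or below 50%.

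**2. Adverse events**

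- 8.6: no new adverse event information after day 30.
- 10.4.1: reporting from consent to completion of an end-of-study report, qualified as by category and as applicable during the study.
- What end of study means: 8.5 collects an End of Study form at the 30-day contact, which favours the short reading. Appendix B.6 defines study completion as the date the final report is issued, which favours the long one. The text does not settle it.

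Capture covers 30 of about 730.5 days of chart time: 30/730.5 = 4.1%. This is a share of time, not of risk. With zero events in n patients, the exact one-sided 95% upper bound is 1 − 0.05^(1/n): 1.2% for n = 250, 2.4% for 121 and 4.8% for 61. Under 8.6 these bounds would apply only to events evident by day 30.

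**3. Call window**

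For a call on day d, the unobserved days before day 30 are max(0, 30 − d).

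- Day 25: 5 days, and 5/30 = 17% for that patient.
- Calls spread evenly over the 11 days from 25 to 35 (assumption): (5+4+3+2+1+0+0+0+0+0+0)/11 = 15/11 = 1.4 days on average, or 1.36/30 = 4.5% of the window.

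**The case against.** The strongest reply is that a 30-day safety window is an openly stated design choice. Patients leave the study at the 30-day contact, the needles are marketed, the patients were already due for EUS-FNA, and no endpoint claims 24-month safety. The seeding entry comes from the commercial directions for use. Late events would be found unevenly because the charts reflect routine care, and after salvage two needles have been used, so attribution to an arm is unclear. All of this stands. It argues for reporting late events separately and descriptively. It does not argue for leaving two passages in conflict, or for leaving the scope of endpoint a unstated.

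On histology, late resection follows management decisions that the aspirate result may have shaped, and tissue taken up to 24 months later is not contemporaneous with the aspirate. This also stands, and it is why late histology should not simply replace the 30-day reference. Protocol 9.3 does allow additional analyses labelled ad hoc, but an ad hoc comparison carries less weight than a prespecified one.

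A reader might go further than the documents allow in four ways:

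- *That later histology is discarded.* It is collected to 24 months. It is not used as reference.
- *That one cut-off does all of this.* The adverse event limit and the histology limit are separate rules in separate sections, and the sentence in 8.6 says nothing about histology.
- *That 17% of 30-day events would be missed.* That figure is unobserved time for one patient called at the earliest date. The documents give no reason for it to differ between arms.
- *That outcomes of events already open at day 30 are lost.* Section 8.6 bars only new information.

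**Conclusion.** The point holds as three separate matters, in descending order of weight.

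1. Endpoint h leaves unused, for patients resected after day 30, the reference that the protocol itself ranks highest and already collects. How many patients this affects cannot be known from the documents. The 6 to 45 range rests wholly on assumed resection rates and timing.
2. Sections 8.6 and 10.4.1 do not agree on how long adverse events are captured, and a related event that first appears at chart review has no clear recording route. The documents do not support predicting a particular count for seeding. They support only the statement that, under 8.6, endpoint a is silent on events not evident by day 30.
3. The day-25 edge of the call window is a small mismatch, up to 5 days for one patient and about 1.4 days on average under an even spread of calls.

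The first two deserve a change because the remedy is cheap and widens what the trial can conclude. The third is a tidy-up.

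**What to change.** **Histology.** Add to Appendix C.3 and SAP 5.1.2 a prespecified analysis of endpoint h in which histology from the chart review replaces the board diagnosis whenever it is available. Report it beside the 30-day version, with the number of patients whose reference changes. List the chart review in the SAP as a data source. Cost: protocol and SAP wording and one further set of tables. Late resection is selective and not contemporaneous, so neither version should be shown alone.

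**Adverse events.** Reconcile 8.6 with 10.4.1 and say what the end-of-study report is. Record events found at the planned chart review that are judged related to the needle or procedure, mark this in the chart-review column of Figure 3, and report them descriptively and apart from the 30-day rate. Cost: an amendment with ethics approval, a relatedness assessment, and reporting timelines that suit retrospective discovery. Ascertainment will depend on routine care, and attribution after salvage will be uncertain. If the sponsor prefers not to do this, state in the protocol and SAP that endpoint a covers only events evident by day 30.

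**Call window.** Open it at day 30, or keep it and report rates to the actual contact date. Cost: one edit.

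No change is needed for follow-up of events already open at day 30.

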9.1. Study Hypothesis and Sample Size Calculation

Sample size was calculated based on assumptions for the primary endpoint as well as for secondary endpoint c):

9.1.1. *Primary endpoint considerations:*

The study hypothesis states that for either of the 19 G Flex and 19 G Arms, the volume of actual aspirated cyst fluid as a ratio (%) of estimated maximal volume is superior by at least 10% compared to that of the 22 G Arm.

The study investigators provided the following experience-based estimate of the primary endpoint (aspirate volume as % of max volume based on EUS image of the cyst):

Figure 4 – Hypothesis Generating References (Primary Endpoint)

Site Investigator	Mean Volume Ratio (%) for 19G and 19Flex needles	Mean Volume Ratio (%) for 22G needles
Investigator 1	80%	50%
Investigator 2	90%	70%
Investigator 3	90% Unilocular cysts, 50% Multi-locular	80%

	cysts, 80% Blended mean	
Investigator 4	90%	90%
Investigator 5	90%	50%
Investigator 6	85%	65%

From the above table, bootstrap method with 10,000 resamples yielded an estimated mean of 67.44% and standard deviation of 15.29% for 22G, and a mean of 85.9% and standard deviation of 4.67% for 19G/19G Flex.

The assumption was made that the mean of the “control group”, namely the 22G arm, will be 67% with a standard deviation of 15.29%.

Two null hypotheses are made:

- H_{01} : Mean volume ratio of 19 G Flex Arm and 22 G Arm are the same
- H_{02} : Mean volume ratio of 19 G Arm and 22 G Arm are the same

The alternative hypothesis is:

- H_1 : Mean volume ratio of 19 G Flex/19G Arm is superior to 22 G Arm

If 50 patients are enrolled in the 19 G Flex Arm and 25 patients each in the 19 G and 22 G Arm, the study will have 90% conjunctive power to detect the rejection of both null hypotheses to demonstrate superiority of the mean volume ratio of 19 G Flex Arm and 19 G Arm to that of 22 G Arm by 10% or more. Thus, a minimum of 100 patients (50+25+25=100) are required.

9.1.2. Secondary endpoint c) considerations:

The study hypothesis states that the EUS-FNA 19 G Flex needle is superior to the EUS-FNA 22 G standard and 19 G standard needles in the secondary endpoint c) measure, which requires access or adequate aspirate volume for two standard assays expected from successful EUS-FNA procedures in PCL assessment indications.

To create a quantitative hypothesis for the study, a meta-analysis was completed of nine literature reports of EUS-FNA success levels in this indication, using standard, non-flexible EUS-FNA needles. The following references outlined in **Figure 5** were used:

Figure 5 – Hypothesis Generating References (Secondary Endpoint c)

Reference	Success ratio	Success Rate
(1) Brugge	109/112	97.3%
(3) Al-Haddad	31/37	83.8%
(5) Larsen	132/251	52.6%

(6) Khalid	76/113	67.3%
(7) Sawhney	84/100	84.0%
(8) Rogart	75/107	70.1%
(9) Hong	60/69	87.0%
(10) de Jong	80/128	62.5%
(11) Repak	38/38	100%

This yields a success rate point estimate of 75% with 95% CI [67% - 90%] (see **Appendix C.1** for details).

The assumption was made that the success level of both “control groups”, namely the 22 G arm and the 19 G Arm, will be 75%.

Two null hypotheses are made:

- H_{01} : Success rate of 19 G Flex Arm and 22 G Arm are the same
- H_{02} : Success rate of 19 G Flex Arm and 19 G Arm are the same

The alternative hypothesis is:

- H_1 : Success rate of 19 G Flex Arm is superior to both 22 G Arm and 19 G Arm

If 121 patients are enrolled in the 19 G Flex Arm and 61 patients each in the 19 G and 22 G Arm, the study will have 80% conjunctive power to detect the rejection of both null hypotheses to demonstrate superiority of the success rate of 19 G Flex Arm to that of both other arms by 16% or more. Thus, a minimum of 243 patients (121+61+61=243) are required.

Details of the sample size calculation are provided in **Appendix C.2**.

